All collected data will be stored electronically with password-protection to prevent unauthorised access to the data. All data and related documents will be kept in a key-locked cabinet for 5 years before being destroyed. Although demographic data will be requested, participants will remain anonymous. For quantitative data, all data will be de-identified at data entry and results will be reported in general terms. For qualitative data, the digital interview files will be deleted after transcription. Data will be de-identified with codes and content separated. Anonymity will be maintained via pseudonyms for direct interview quotes used in the reporting of findings.

For ethical consideration, our research team will provide opportunity for the elderly in the control group who receiving plush toy. They can choose to partake two 50-minute sessions of group-based Paro interventions to experience interactions with Paro after completing their intervention and follow up.

V. Expected difficulties encountered and solutions

1. Difficulties for participant's recruitment and active engagement data collection

This study will conduct 6 weekly sessions of Paro intervention in LTC facilities. Older adults may feel anxious about interaction with a Paro or withdraw from the intervention. For dealing with this potential problem, the possible solutions are as below:

- (1) The research team will hold a briefing to explain the research process to the participating institutions in order to attract the participation of the heads of the institutions.
- (2) Introducing the Paro to family and encourage family and workers interacting with the Paro. Also, encouraging participants share their experiences with his/her friends.
- (3) Provide incentives or motives for participants and explaining the research procedure and potential benefits for them. The research team will show a Paro video or demonstrate Paro interaction to participants and facilities to introduce how the Paro interact with other older adults and share with experiences to using it.

2. Difficulties in quality assurance and quality control in Paro research

As a limited number of Paro, each round will plan to recruit 6 participants. The research team will extend the study periods to recruit enough participants. For controlling the research quality, the possible solutions are as below:

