- (1) *To increase the quality and consistency of interaction with Paro.* Each facility will recruit two volunteering care staff to participate in the study. Staff will receive 1 hour of Paro interactive training. Each care staff will provide incentives and motives to increase motivation to partake this study.
- (2) *For reducing the interference or contamination among the four groups.* This study will recruit control group and experimental groups in different levels to prevent interference among groups receiving intervention at the same time in

the same facility.

- (3) *To reduce the human interferences.* In order to establish a research consensus among institutional staff, we will provide a 60-minute course to workers in participating facilities, the purpose of which is to help them to familiarize with our programs and procedures

VI. Expected the contribution of the Research

This study will thoroughly examine the effect of Paro intervention on oxytocin level, dopamine and HRV for specific attachment orientation older adults with dementia. This is the first study we know of to utilize a rigorous research design to examine the effect of intervention and explore the relationship between different attachment orientation older people and Paro. The findings of this study will provide strong evidence and advance knowledge of the mechanism of Paro intervention in LTC of Taiwan and be able to link this result to international studies. The findings of the research will publish in international journals.

VII. Expected Contribution of Research to Personnel

There are regular training and interdisciplinary meetings for all research staff to strengthen their research skills, as well as expand their knowledge for newly aged care model such as innovated technological devices and robots for older adults. The staff will conduct research capacity training prior to the study, including Paro intervention, and data analysis. Research members will recognize measurements of FTT and HRV and learn how to cooperate with interdisciplinary experts. These skills will help members to foster teamwork and interdisciplinary knowledge and expand integration of knowledge systems such as nursing, psychological and robotic technology. The above training will help members to advance capabilities to be an independent research, behavioral observer, and a competent analyzer.

Study 2:

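### Studies 1 and 3: the steps that promote Paro within facilities are not limited by arm or time, so they may expose controls and work against the plan's own contamination control

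*Combined protocol and SAP*

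**What the plan says.** Study 1, section V.1, and Study 3, section IV.1, give the worry: "Older adults may feel anxious about interaction with a Paro or withdraw from the intervention". The remedies listed there include:

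- "Introducing the Paro to family and encourage family and workers interacting with the Paro. Also, encouraging participants share their experiences with his/her friends";
- "The research team will show a Paro video or demonstrate Paro interaction to participants and facilities".

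No arm, place or period is attached to any of them.

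The next subsection (Study 1, V.2; Study 3, IV.2) has an item headed "For reducing the interference or contamination among the four groups". Its remedy is to recruit control and experimental groups on different levels, so that groups running at the same time in one facility do not interfere with each other. What a level is (floor, ward, grade of care) is not said. The same subsection states: "Each facility will recruit two volunteering care staff to participate in the study. Staff will receive 1 hour of Paro interactive training".

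Controls receive the facility's usual activities (Study 1, II.5; Study 3, I.5). Outcomes are assessed blind by a different research assistant (Study 1, II.8; Study 3, I.7). The Ethical Considerations sections add, for controls: "They can choose to partake two 50-minute sessions of group-based Paro interventions to experience interactions with Paro after completing their intervention and follow up".

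**The concern.** The plan accepts that both arms may live under one roof and wants them kept apart. A page earlier it encourages workers to handle Paro, participants to talk about it, and the team to show it around the facility. The workers on site are also the people from whom the control arm's usual activities come, and the two Paro-trained staff are not barred from leading those activities. A participant's friends may be fellow residents in the control arm.

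Two things are at stake. Controls who meet Paro during follow-up are no longer a clean usual-activities comparison. And participants who have been encouraged to talk about Paro are more likely to mention it to the assessor who is meant not to know their arm. The analysis is by intention to treat (Study 3, I.8), and the plan does not provide for recording control exposure to Paro, so neither the extent nor the effect of any leakage could be examined afterwards.

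**Working it through.** **The plan's own figure.** Study 1, II.4 gives 120 participants, 60 per arm, with no effect size, SD, power or dropout, so there is nothing to reproduce. Solving backwards with the two-means normal approximation at two-sided alpha 0.05 (sidedness is not stated) and 80% power: d = (1.960 + 0.842) × √(2/60) = 0.51. No contamination allowance can be read from the figure.

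**The texts side by side.**

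| Step | Limited to Paro arm? | Limited in time? | Does separation by level block it? |
|---|---|---|---|
| Family and workers handle Paro | No | No | Not for workers, who are not said to be confined to a level |
| Participants share experiences with friends | No | No, and there is nothing to share until sessions start | Not for friends on another level |
| Video or demonstration | No, it names participants and facilities | No | Not if given facility-wide |
| Two Paro-trained staff per facility | Not addressed | Not addressed | Not addressed |
| Deferred sessions for controls | Controls only | After each control's own follow-up | Covers only groups running at the same time |

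Both the engagement list and the contamination list are introduced as possible solutions, so neither outranks the other.

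**Deferred sessions.** Rounds are planned at 6 participants, with the study period extended to fill the sample. That is 60/6 = 10 rounds if the six are all Paro participants, or 120/6 = 20 if both arms are counted. The number of facilities is not given. If any facility hosts more than one round, early controls could be having Paro sessions while later controls there are still being measured.

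**Outcomes.** The Study 1 primaries are oxytocin, finger tapping and HRV. The Study 3 primaries are the MMSE and computerised executive tasks. Loneliness, depression and well-being are secondary in Study 3 and rest on self-report, so they are the most exposed to talk about Paro. Study 2 repeats the text (V.1, V.2) but studies only the experimental group, so it has no between-arm contrast to bias.

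**Illustration of size; every input except n is assumed.** If controls receive on average a share c of the Paro effect, the expected difference is d(1 − c). Power ≈ Φ(d(1 − c) × √(n/2) − 1.96), with n = 60 per arm and no dropout or clustering. For d = 0.50 and c = 0.20: 0.40 × √30 − 1.96 = 0.23, so power is 59%.

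| Assumed d | c = 0 | c = 10% | c = 20% | c = 30% |
|---|---|---|---|---|
| 0.30 | 38% | 32% | 26% | 21% |
| 0.50 | 78% | 69% | 59% | 48% |
| 0.80 | 99% | 98% | 94% | 87% |

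This shows what dilution would cost. It does not estimate how much would occur.

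**The case against.** The engagement steps are offered as possibilities, and their stated target is anxiety about Paro and withdrawal from the intervention, which points mainly to the Paro arm. Nowhere does the plan say that a control handles Paro or that anyone takes it to controls. Its literature review pairs friends with family as visitors to the home, so the friends in question may be outsiders. Hearing about Paro is not the same as a facilitated group session. There are other safeguards: a weekly check on both groups, a 60-minute course for facility workers, scripted sessions in which the research assistant hands out Paro, and a limited number of units. Finally, removing the steps could raise withdrawal, and with last observation carried forward as the missing-data method that is a bias risk of its own.

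Most of this stands as a limit on how strongly the point can be put. It does not settle the conflict. The listed safeguards do not say which arm, place or period the engagement steps belong to. The weekly check is described as a fidelity check and is not said to record exposure. If only the Paro arm was meant, a phrase would say so. The withdrawal argument is a reason to restrict the steps rather than abolish them.

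**Conclusion.** The engagement steps and the contamination control pull against each other in Studies 1 and 3 and need to be reconciled. What follows is a risk: possible control exposure and possible unblinding of the assessor. The likeliest effect is a contrast pulled toward no difference, mainly on the three self-reported secondary scales. The size cannot be computed, because the documents give no contamination rate, effect size or number of facilities.

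A reader might infer more, and the documents do not support it:

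- *That the contrast is biased.* No control exposure is described, and the direction is not fixed. Controls who have seen Paro and must wait for it could report worse mood, which would widen the difference.
- *That controls are shown Paro before allocation and then denied it.* The timing of the demonstration is not stated. Given before allocation, it would reach both arms alike. Controls are offered Paro after follow-up, so access is delayed, not refused.
- *That the deferred sessions cap the dilution at 2 × 50 = 100 minutes against 6 × 30 = 180, about 56%.* Those sessions follow a control's own last assessment and cannot dilute that person's data, and a ratio of minutes is not a fraction of effect.

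This is a cheap improvement worth making, not a demonstrated flaw in the results.

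**What to change.** 1. In Study 1, V.1 and Study 3, IV.1, confine handling of Paro by family and workers to the Paro arm's own sessions and families until the facility's last T3 assessment.
2. In the same sections, drop the encouragement to share experiences, or restrict it so that it reaches neither control residents nor the assessor.
3. If a demonstration is used before allocation, give it identically to all participants before T0. Otherwise give it only to the Paro arm.
4. In Study 1, V.2 and Study 3, IV.2, define the levels, and state that Paro-trained care staff neither lead control-arm activities nor assist with outcome assessment.
5. In the Ethical Considerations sections, start deferred control sessions only when no control in that facility has an assessment due.
6. Log any control exposure to Paro at the weekly check already planned (integrated project, section VIII, item 3; Study 3, Work Projects, item 3).

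The cost is protocol wording and one extra item on the weekly check. Paro is promoted a little less within facilities, and some controls wait longer for their deferred sessions. Familiarisation for the Paro arm, which answers the worry about anxiety and withdrawal, is kept.

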However, existing research pointed out that the effectiveness of social robot (Paro) on people with dementia has shown inconsistent results. Previous studies have also found that different emotional attachments between human and Paro have shown different psychological effects for older adults. However, these conclusions still lack empirical research support. Therefore, the integrated project will conduct three sub-projects to examine the changes in biomedical, cognitive, and mental health of specific attachment older adults with dementia after receiving group-based Paro intervention. Study 1 will use a pilot randomized controlled trial to examine the effect of Paro intervention on oxytocin, dopamine and HRV variations for specific attachment older adults with dementia. A randomized controlled trial, single-blind, two parallel groups, and repeated measures design were used to examine the effects of Paro intervention on neurobiological changes for specific attachment older adults with dementia at before, during and after the intervention. A sample of 120 older adults with dementia who are 65 years or older living in long-term care will be invited. Older adults will be randomly assigned to two groups: experimental group or control group. The outcomes will be assessed based on the change of dopamine and HRV at baseline, 3rd week during the Paro intervention, the end of intervention (6th week), and the 1 month after the Paro intervention. Furthermore, the change of oxytocin will be assessed at two time points: baseline and the end of Paro intervention. Study 2 will focus on the 60 participants of the 2 experimental groups. A mixed method combined qualitative and quantitative research design will be used to explore the participating experience, group interaction, and its' association with mental health. Based on study 1 design, the outcomes of study 3 will be assessed based on the change of cognitive, executive functions, loneliness, depression, and well-being at the same points of study 1.

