Paro interventions are based on human-animal interactions aimed at providing physiological, psychological, and social benefits. Physiological effects are triggered through sensory stimulation with Paro such as stroking, hugging, and kissing, and can result in a reduction in stress-hormone levels (Shibata et al., 2004) and lower blood pressure and heart rates (Robinson et al., 2015). Psychological effects are experienced through the comfort and joy derived during close interaction (Chang et al., 2013). Social benefits are provided through engagement in activities (Cohen-Mansfield et al., 2010). In this study, Paro will be used as a psychosocial intervention with the aim to examine its effect on neurobiological variations as well as cognitive functions and group process changes in specific attachment older adults with dementia. We hypothesized the above biomarkers demonstrated in previous studies which would be correlated to cognitive functions, trust and stress relieving, would also present in geriatric dementia

patients.

II. Method

1. Aims

The aims of this study is to examine the effect of the Paro intervention on oxytocin, dopamine and HRV for attachment-specific people with dementia.

2. Objectives

- (1) To examine the effect of Paro intervention on oxytocin level for the older people with dementia.
- (2) To examine the effect of Paro intervention on dopaminergic activities in terms of FTT for older people with dementia.
- (3) To examine the effect of Paro intervention on HRV changes, naming autonomic functions for older people with dementia.
- (4) To examine the effect of Paro intervention on the associations of the above neurobiologically variations and cognitive functions
- (5) To examine the effect of Paro intervention on the associations of the above neurobiologically variations and group process

3. Research design

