To explore the interaction experience and its' relationship with the change of mental health undergoing group-based Paro intervention on people with dementia: Group process analysis

Abstract

Social robots have been validated as a therapeutic modality to provide stimuli to reduce the negative emotions and to improve the mental health for people with dementia. Different psychological effects for older adults those who had different emotional attachments styles between human and Paro had been found. However, these conclusions still lack empirical evidence and consistent results about the effectiveness of group-based social robot (Paro) on people with dementia.

Therefore, this integrated study will use a randomized controlled trial (RCT) to examine the process and outcomes of a weekly 6-session group-based Paro intervention. The association of group process and mental health for specific attachment older adults with dementia will be validated. A RCT, single-blind, four parallel groups, and repeated measures design were used to examine the effects of Paro intervention at before and after the intervention. Sixty older adults will be randomly assigned to two groups: experimental group or control group. In the subproject 2, we particularly focus on the 60 participants of the experimental group with dementia who are 65 years or older living in long-term care. A mixed method combined qualitative and quantitative research design will be used to explore the participating experience, group interaction, and its' association with mental health.

Thematic analysis will be conducted by the video-recorded, group process, memo and verbatim of 6 weekly 30-minute session Paro intervention after obtaining the inform consent of the participants. The group climate and satisfaction will be assessed at the end of 1st, 3rd, 6th session by group observers, and participants, respectively. The correlation will be examined between the group process with the change of loneliness and depression at pre- and post- intervention that conducted by subproject 3. We expect to assure and contrast the process and group effectiveness in this subproject. The study findings will provide empirical result to utilize the group-based Paro intervention for the older people with dementia. A strong evidence will be established to promote the alternative therapy into different attachment styles of dementia care, combining the

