This is a mixed method study that combined a qualitative and quasi-experimental design with two parallel groups. In the experimental groups, content analysis will be used to explore the group interaction experience with video-recorded and transcribe verbatim. A between-within subjects analysis of variance design will be used to assess the 6-session Paro intervention on the group process variables which include group climate and group satisfaction. Relationship between changes of group process and mental health by groups will be examined with a correlation analysis. Outcomes of interest measures will include group process at three time points: the first, third, and sixth session intervention; and mental health will be measured before the intervention and (T0) the end of intervention (6-session, T1).

The purpose of this study is to explore the relationship of group process and mental health undergoing group-based Paro intervention on older adults with dementia in LTC. The research design is shown in Table 1.

Table 1 Research design for exploring the group process and outcomes of group-based Paro intervention

Group	T0	Intervention / Group process	T1
Experiment group	O ₁	X (1 st , 3 rd , 6 th session)	O ₂

Note: T0 (before the intervention); T1 (after 6th session intervention); X (the group-based Paro intervention will be video-record, the group process will be analyzed by content analysis, and the group climate and satisfaction at session 1st, 3rd, and 6th will be assessed); O1, O2: Outcomes of measurement include the loneliness and depression assessment.

5. Sample size, Sampling, Settings, and Participants Recruitment

In the subproject 2, will focus on the participants in the experimental group (n=60). Contact has been made with the Directors of the LTC facilities who have expressed their interest in being involved in the study. Directors will invite older adults who meet the inclusion criteria to participate in this study.

The inclusion and exclusion criteria of elderly participants will be the same study 1.

6. Intervention

The Paro intervention will be the same study 1.

7. Outcome measures

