Differences between the pre and post-test in relation to outcome measures (loneliness and depression) will be used a mixed between-within subjects analysis of variance design to assess the immediate effects of the 6-week Paro intervention on mental health. The association of group process variables (group climate and satisfaction) and mental health will be examined for different attachment orientations of older adults living LTC facilities. A p value $< .05$ will be taken as the level of

statistical significance. The 95% confidence interval around the differences will be calculated.

III. Expectation Outcome

We expect to explore the group process and its' relationship with mental health (depression and loneliness) of 6-session group-based Paro intervention, and beneficial and hindering group experience of older adults with dementia.

IV. Ethical Considerations

Ethics approval for both phases of the study will be sought from Cheng-Kung University Human Research Ethics Committee and prior to the commencement of the study. Ethics approval for the study will also be sought from the participating LTC facilities in Taiwan prior to the commencement of the study. The researcher will inform the participants about the aims and objectives of the research study and what their participation will involve. Participants will be assured that (a) their participation will be on a voluntary basis and they are under no obligation to participate; and (b) they are free to withdraw from the study at any time without explanation, penalty or compromising their relationship with the LTC. A signed consent form will be sought from each participant. There are no foreseeable risks associated with participation in the intervention for participants.

All collected data will be stored electronically with password-protection to prevent unauthorised access to the data. All data and related documents will be kept in a key-locked cabinet for 5 years before being destroyed. Although demographic data will be requested, participants will remain anonymous. For quantitative data, all data will be de-identified at data entry and results will be reported in general terms. For qualitative data, the digital interview files will be deleted after transcription. Data will be de-identified with codes and content separated. Anonymity will be maintained via pseudonyms for direct interview quotes used in the reporting of findings.

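### Study 2 tests an effect of Paro on loneliness and depression, but its stated sample holds only the Paro arm and its design labels conflict

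*Combined protocol and SAP*

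**What the plan says.** **Analysis.** Study 2, II.8(3) Quantitative data analysis, says of the pre/post differences in these two outcomes that they "will be used a mixed between-within subjects analysis of variance design to assess the immediate effects of the 6-week Paro intervention on mental health". It names no between-subjects factor for this ANOVA.

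**Sample.** Study 2, II.5 reads "In the subproject 2, will focus on the participants in the experimental group (n=60". The Study 2 abstract agrees: "we particularly focus on the 60 participants of the experimental group with dementia who are 65 years or older living in long-term care". Table 1 in II.3 has a single row, the experiment group, measured before and after the intervention.

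**Labels that do not fit that sample.**
- II.3 Research design: "This is a mixed method study that combined a qualitative and quasi-experimental design with two parallel groups". The second group is never identified.
- Study 2 abstract: "A RCT, single-blind, four parallel groups, and repeated measures design were used to examine the effects of Paro intervention at before and after the intervention". The next sentence has sixty people randomised between Paro and control, which would be 30 per arm.
- Project abstract: "Study 2 will focus on the 60 participants of the 2 experimental groups". It gives the same 60 people but speaks of two experimental groups.

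**Where the controlled data are.** Study 3, I.7 lists loneliness and depression as secondary outcomes, measured at baseline, week 3, week 6 and follow-up in both randomised arms. The Study 2 abstract says that its change scores come from subproject 3.

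**A related objective.** Study 1, II.2, objective 5: "To examine the effect of Paro intervention on the associations of the above neurobiologically variations and group process".

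**The concern.** A mixed between-within ANOVA supports a statement about a treatment only if treatment arm is the between-subjects factor. The term of interest is then arm by time. With only treated people in the data, what remains is change over time. Over six weeks in long-term care residents, scores can move because of natural drift, because the same questionnaires are repeated, or because people with extreme baseline scores move back towards the mean.

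At stake is how one result is labelled. The project could carry two statements about Paro and loneliness or depression, drawn from overlapping data. One would be randomised (Study 3). The other would be uncontrolled (Study 2) but described in the same causal words.

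**Working it through.** **1. Reproduce the sample figure.** Study 1, II.4 recruits 120 people and allocates 60 to each arm. 120 × 1/2 = 60. Study 2's n=60 is therefore exactly the Paro arm, and no controls are left in it. If the abstract's other sentence were followed (sixty randomised to two groups), each arm would have 60/2 = 30, which contradicts the 60 experimental participants given in the same abstract.

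**2. Which reading does the text favour?** The Chinese abstract, the project abstract, the Study 2 abstract and II.5 all give 60 experimental participants, and Table 1 has only that group. No sentence places identified control participants in the Study 2 data set. The Paro-only reading is the better supported.

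**3. What can be estimated on that sample.** Without an arm factor, the only term that could be read as Paro is the within-person time effect. A between factor such as therapy group or attachment type would make the ANOVA computable. Its interaction would compare subsets of treated people, and its time effect would still have no untreated comparator.

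**4. Size, as an illustration.** The documents give no SD, drift or correlation, so these are assumptions: Paro has no effect; the background shift d is 0.1 to 0.3 SD; the pre-post correlation ρ is 0.5 to 0.8; the test is two-sided at 0.05 (the plan gives 0.05 but not the sidedness); clustering within the therapy groups of 6-8 is ignored.

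- SD of change = √(2(1−ρ)), in units of the outcome SD.
- Noncentrality of the paired t test = d × √60 / SD of change, with 59 df.
- Example, d = 0.2: at ρ = 0.5, SD of change = 1.000 and noncentrality = 0.2 × 7.746 / 1.000 = 1.55. At ρ = 0.8, SD of change = 0.632 and noncentrality = 0.2 × 7.746 / 0.632 = 2.45.

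Probability of p<0.05 in the one-arm test:

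| ρ | d = 0.1 | d = 0.2 | d = 0.3 |
|---|---|---|---|
| 0.5 | 11.9% | 33.2% | 62.8% |
| 0.6 | 13.6% | 39.9% | 72.4% |
| 0.7 | 16.6% | 50.3% | 83.9% |
| 0.8 | 22.6% | 67.3% | 95.1% |

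The rates are the same whichever way the shift runs. A drift towards worse scores would also be significant, but nobody would read it as benefit.

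**5. The controlled alternative.** With the same drift in both arms, an arm-by-time test with 60 per arm rejected in 4.9% to 5.1% of 20,000 simulated trials (d = 0.2 and 0.3, ρ = 0.5 and 0.7). At 80% power it detects a between-arm difference in change of about 0.52, 0.40 or 0.33 SD at ρ = 0.5, 0.7 or 0.8, ignoring clustering and dropout.

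**The case against.** The strongest defence is that the text is contradictory, not plainly uncontrolled. The Study 2 abstract calls the design an RCT with a control group, and II.3 speaks of two parallel groups. If controls were meant to be in this ANOVA, the analysis is sound and the sample statement and Table 1 are what is incomplete. This stands in part: a reader might infer that an uncontrolled analysis is certain, and the documents do not establish that. They establish a conflict, with most of the text on the Paro-only side.

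Second, some objectives are stated by groups, and the analysis section mentions attachment orientations, so a between factor may exist. It would make the ANOVA computable, so it is too strong to say that the model cannot be run. But neither factor is named for this ANOVA, and neither supplies a comparator for Paro.

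Third, Study 2 has no efficacy objective. Its aim is process and its relation to mental health, its primary outcome is qualitative group experience, and the Chinese abstract uses the Study 3 change scores only for correlation. A reader might infer that the project will publish the pre-post change as efficacy evidence, or that it lacks a randomised comparison for these outcomes. The first is a risk created by one sentence, not a stated plan. The second is wrong, because Study 3 has the comparison.

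Fourth, the rejection rates rest on assumed drift and correlation. That is so: they show how a one-arm test behaves, not what will happen in this trial.

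Finally, Study 1 objective 5 has no ANOVA attached. It is a loosely worded association objective, and treating it as the same fault would go too far.

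**Conclusion.** The point holds as a conflict between Study 2's analysis, its sample and its design labels. As written, the analysis claims an effect of Paro that the stated sample cannot support. That conclusion needs no assumption beyond the sample statement and Table 1. Its possible size does: under the assumptions set out above, the chance of a significant change with no Paro effect runs from about 12% to 95%, where the controlled test stays near 5%.

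The damage is limited to one sentence about non-primary outcomes of Study 2. The randomised comparison in Study 3 and the process analyses, which need no control arm, are untouched. It should be corrected before analysis, and there is no reason to leave it.

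**What to change.** 1. **Study 2, II.8(3).** Remove the ANOVA as a test of Paro's effect on loneliness and depression. Refer instead to the arm-by-time comparison of all 120 randomised participants in Study 3, baseline to week 6. Week 6 is T2 in Study 3 but T1 in Study 2, so name the visit by week.
2. **Study 3, I.8 Data analysis.** Name loneliness and depression in the model. At present its arm comparison names only oxytocin, dopamine and HRV. The mental well-being variables are covered only by the general ANOVA sentence in the Study 3 abstract and research design.
3. **Scope of Study 2.** Limit it to change in group climate and satisfaction across sessions 1, 3 and 6, and to associations between process and change within the Paro arm, stated as non-causal. Report any Study 2 pre-post change as descriptive. If therapy group or attachment type is meant as a between factor, say so and say what it tests.
4. **Labels.** Reconcile the number of groups and the sample in the project abstract, the Study 2 abstract and Study 2, II.3 and II.5.
5. **Minor wording.** Restate Study 1 objective 5 as an association within the Paro arm, since group process is recorded only there.

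The cost is wording. No data are lost, no visits are added and no participants are affected.
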